## **6. STUDY POPULATION**

Prospective approval of protocol deviations to recruitment and enrollment criteria, also known as protocol waivers or exemptions, is not permitted.

Study patients are considered enrolled into the study using a deferred consent procedure or another legally acceptable local consent procedure in this special ICU situation.

### **6.1. Phase II**

#### **6.1.1. Inclusion Criteria**

Patients must have met all the following criteria at screening and at enrollment to be randomized into Phase II of the study:

1. At least 18 years of age or older
2. Clinically evident or otherwise confirmed severe pneumonia as evidenced by at least one of the following criteria:
3. Chest X-ray or computed tomography (CT) scan or magnetic resonance imaging (MRI) with pulmonary infiltrates consistent with pneumonia
4. Clinical history in past 14 days of newly developed severe shortness of breath (> 29 breaths / minute) in the absence of oxygen supply or spontaneous peripheral oxygenation  $\leq$  92 with

need for oxygen supply, or need for non-invasive or invasive ventilation (in conjunction with a positive test for SARS-CoV-2 infection)

5. Oxygenation index at time of enrollment ( $\text{PaO}_2 / \text{FiO}_2$ )  $\leq 250$  and  $\geq 100$  in supine position
6. SARS-CoV-2 infection confirmation (tested positive in last 14 days or test results to be obtained within 24h after enrollment, both with locally available test system).
7. No use OR stop of any corticosteroid treatment at time point of enrollment (topical treatment and systemic dose of  $\leq 10\text{mg}$  prednisone / day equivalent allowed)

#### 6.1.2. Exclusion Criteria

Patients who fulfilled any of the following criteria at screening were not eligible to participate in Phase II of the study:

1. Oxygenation index at time of enrollment ( $\text{PaO}_2 / \text{FiO}_2$ )  $< 100$  or  $> 250$  in supine position
2. Intubated  $> 48\text{h}$  at time point of enrollment
3. Patients who demonstrate an improvement in past 24h prior to enrollment in oxygenation and ventilation / support parameters which indicate an expected resolution of lung dysfunction in the next 24h without additional intervention according to judgment of the investigator with one or more of the following parameters present:
4. Improvement in oxygenation index of  $> 30\%$  relative to previous measure (last 24h in supine position)
5. Extubation if intubated before
6. Known history of chronic obstructive pulmonary disease (COPD) (GOLD category C or D)
7. Known history of chronic dialysis OR received renal replacement therapy in past 14 days
8. Received new other biologic treatment attempt for COVID-19 in the past 14 days
9. Received treatment with a viral replication inhibitor in past 3 days
10. Known hypersensitivity to IFX-1 or any other ingredient of the study medication
11. Known pregnancy
12. Received organ or bone marrow transplantation in past 3 months
13. Known mechanically resuscitation in past 14 days
14. Patient moribund or expected to die in next 12h according to the judgment of the investigator
15. Patients otherwise considered restricted from receiving full supportive care (including ICU support)
16. Existing diagnosis of progressed cancer or other life-limiting disease with life expectancy  $< 6$  months
17. Known to have received anti-cancer therapy for oncological disease in past 4 weeks

18. Known severe congestive heart failure (New York Heart Association [NYHA] Class III-IV; see Appendix 8)

## 6.2. Phase III

### 6.2.1. Inclusion Criteria

Patients must meet all the following criteria at randomization to be enrolled into Phase III of the study:

1. At least 18 years of age or older
2. Patient on invasive mechanical ventilation (but not more than 48h post intubation at time point of first IMP administration)
3. Patients with a PaO2 / FiO2 ratio of < 200 and > 60 at randomization (one representative measurement within 6h before randomization)
4. SARS-CoV-2 infection confirmation (tested positive in last 14 days before randomization with locally available test system)

### 6.2.2. Exclusion Criteria

Patients who fulfill any of the following criteria at randomization are not eligible to participate in Phase III of the study:

1. Intubated > 48 h at time point of first IMP administration
2. Expected stop of invasive ventilation or expected extubation in the next 24h without additional intervention according to judgment of the investigator
3. Known history of chronic dialysis OR received renal replacement therapy in past 14 days OR anticipated to receive renal replacement therapy within 24h after randomization
4. Known history of progressed COPD as evidenced by use of daily maintenance treatment with long-acting bronchodilators or inhaled/oral corticosteroids for > 2 months
5. Treatment of COVID-19 with investigational antibody treatment(s) which are not approved or not included in locally adopted treatment guidelines (e.g., WHO guidance, National Institutes of Health [NIH] COVID-19 treatment guidelines) for this indication in the past 7 days (Note: Antibody treatment[s] given within past 7 days for pre-existing diseases, other than COVID-19, are allowed.)
6. At time point of randomization, treatment of COVID-19 with investigational treatments which are not approved or not included in locally adopted treatment guidelines for this indication (e.g., WHO guidance, NIH COVID-19 treatment guidelines), including SARS-CoV-2 multiplication inhibitor(s) or immunomodulator(s). (Note: If a locally adopted treatment guideline recommends drugs such as remdesivir, dexamethasone, or anticoagulation, this would be allowed. Adopted guidelines and updates must be documented at study initiation and throughout the conduct of the study.)
7. Received cytokine adsorption therapy in past 3 days

8. Known hypersensitivity to IFX-1 or any other ingredient of the study medication
9. Serum or urine pregnancy test positive before randomization (required for women of childbearing potential)
10. Received organ or bone marrow transplantation in past 3 months
11. Known cardio-pulmonary mechanical resuscitation in past 14 days
12. Patient moribund or expected to die in next 24h according to the judgment of the investigator
13. Known to have received anti-cancer therapy for hemato-oncological disease in past 4 weeks  
OR known to have active malignant disease at time point of randomization
14. Known severe congestive heart failure (corresponding to e.g. NYHA Class III-IV, left ventricular ejection fraction <40%; see Appendix 8)
15. Known history of chronic liver disease (Child-Pugh B or C; see Appendix 11)
16. Participating in or has participated in other investigational interventional studies (drug or device) within the last 7 days before randomization

### 6.3. Deferred Consent and Other Forms of Informed Consent

In the Netherlands and Germany, we ask for deferred consent for patients in need of intensive care and we appeal to the emergency procedure for consent in medical research as stated in Article 6, Paragraph 4 of the Medical Research Involving Human Subjects Act (WMO, the Netherlands), §41 (1) of the Medicines Act (AMG, Germany), and other applicable country specific regulations, because of the following reasons:

It is very likely that the severity of the disease (severe pneumonia/acute respiratory distress syndrome) will result in a large proportion of patients unable to provide informed consent before the beginning of the trial either in oral or written form, mainly due to being on a ventilator or treated with drugs with sedative effects. COVID-19 related pneumonia resulting in the need for intensive care is a fast progressing disease. It requires immediate adequate treatment that cannot be postponed. So far, no treatment has been shown to address the underlying neutrophilic, inflammatory lung damage. Since IFX-1 blocks C5a, it has the potential to block neutrophil attraction to the lung. Moreover, it has been shown that COVID-19-related severe pneumonia is linked to extremely high C5a blood levels and related to a worse outcome of patients ([Gao et al. 2020](#)). In an ongoing study testing the biosimilar C5a antibody BDB-1, the first 2 patients treated showed a good recovery after being treated. Taken together, there is a possibility that treatment with IFX-1 will provide benefit specifically for patients with COVID-19-related severe pneumonia that require intensive care.

These severely ill patients are incompetent to give informed consent, and obtaining informed consent from a legal representative/relative may be almost impossible due to the current COVID-19-caused quarantine measures. Time to get informed consent from legal representatives/relatives will take at least half day, even by an experienced research team.

Patients have to be randomized at the ICU after inclusion and exclusion criteria have been checked and patients have been found to be eligible.

In the Netherlands, if the patient is incompetent to provide informed consent and a legal representative/relative cannot be reached in time, the investigator examines the patient, confirms and documents the patient's inability to provide consent as well as the urgency of participating in the trial with possible benefit to the patient. Informed consent from the patients, their relatives or their legal representative will be requested at the earliest appropriate time thereafter as applicable in the participating country. At minimum, the attempt of contacting the patient's relatives and the result of the contact will be documented in the patient's file.

In Germany, the investigator examines the patient and, if the patient is not able to consent, confirms and documents together with a consulting physician the patient's inability to provide consent as well as the urgency of participating in the trial with possible benefit to the patient. Informed consent from the patient will be requested at the earliest appropriate time thereafter. A further option in Germany may be the signing of the informed consent by the patients' legal representative.

In other participating countries where a deferred consent procedure is not legally acceptable, specific requirements will be laid out that will describe the country-specific legally acceptable procedure for retrieving consent from patients who are incompetent to provide consent or their relatives or their legal representatives, whatever will be applicable.

The hypothesis is that this group of intensive care patients can potentially benefit from participating in this study. While patients are exposed to the possible side effects of IFX-1, they will also receive SOC in Phase III.

#### **6.4. Screening Failures**

Screening failures are defined as patients who do not meet the criteria for participation in this study and thus, are either not randomized/assigned to IMP or randomized in error and do/did not receive IMP. Screen failure data for not randomized patients will not be recorded in the eCRF, for those patients who are randomized in error, screen failure data are to be recorded in the eCRF.

Rescreening does not apply to this study.

#### **6.5. Meals and Dietary Restrictions**

Not applicable.

## 7. STUDY DRUG(S) AND ADMINISTRATION

### 7.1. Investigational Medicinal Product

The IMP is defined as the investigational treatment IFX-1 and Placebo-to-match (Placebo) that is intended to be administered to a study patient according to the study protocol.

#### 7.1.1. Packaging and Labelling of Investigational Medicinal Product

IFX-1 concentrate solution for infusion will be supplied in 20 mL glass vials at a concentration of 10 mg/mL (200 mg per vial) for reconstitution and IV administration. Apart from IFX-1, the solution will contain sodium chloride, sodium phosphate, and polysorbate 80.

Placebo concentrate solution for infusion will be supplied in 20 mL glass vials for reconstitution and IV administration. The solution will contain sodium chloride, sodium phosphate, and polysorbate 80.

IFX-1 and Placebo will be packaged in cartons and labeled in accordance with all legal requirements. Each carton will contain 4 vials of IFX-1 or 4 vials of Placebo. Each carton and each vial will be labeled with a multilingual booklet label or a single panel label as applicable.

#### 7.1.2. Storage, Handling, and Accountability

Vials of IFX-1 and Placebo must be stored in a refrigerator at 2°C to 8°C (35.6°F to 46.4°F) in their original cartons to protect from light and must not be frozen or shaken. All supplies of IFX-1 and Placebo must be stored separately or segregated from other study supplies and site stock in a dedicated locked facility with access limited to authorized personnel. All storage facilities must be temperature controlled and monitored and compliant with applicable regulatory requirements.

An established and validated local temperature management system with temperature logs should be used to record the storage temperature. If this is not possible, the study site will be provided with a temperature record form by the Contract Research Organization (CRO) and the site personnel will maintain temperature records for the entire duration of the study. At a minimum, the daily (working day) minimum and maximum temperatures must be documented.

Any deviation from the specified temperature range must be documented and reported within 24 hours (or the next working day). Further instruction on the management and reporting of temperature deviations is provided in the Investigator Manual (or equivalent document).

The investigator or designee must confirm appropriate temperature conditions have been maintained during shipment for all IMP received and any discrepancies are reported and resolved before use of the IMP.

Only patients enrolled in the study may receive IMP and only authorized site staff may prepare and administer IMP. The IMP must be prepared in a controlled area in accordance with local regulations/ requirements for reconstitution of products for IV administration.

The investigator, institution, or the head of the medical institution (where applicable) is responsible for the correct storage of IMP, IMP accountability, reconciliation, and record maintenance (i.e., receipt, reconciliation, and final disposition records).

Further guidance and information for the final disposition of unused IMP are provided in the Investigator Manual (or equivalent document) provided by the CRO.

#### **7.1.3. Drug Preparation and Administration Instructions**

The IFX-1 and Placebo for infusion will be reconstituted (prepared) in a controlled area at the study site or at the study site's pharmacy, in accordance (compliance) with applicable local regulations/ requirements for reconstitution of products for IV administration.

The reconstituted IFX-1 or Placebo should be used within 4 hours after dilution when stored at room temperature. Otherwise, the reconstituted IFX-1 or Placebo has to be stored at 2°C to 8°C (35.6°F to 46.4°F) and used within 24 hours; if the reconstituted solution is stored in a refrigerator, it must be left to acclimatize to room temperature prior to administration. Details for the preparation of the reconstituted solution will be provided in the Investigator Manual (or equivalent document).

The number of unused, partially used, and empty vials will be documented accurately, and the vials will be kept at the site until further notice by the Sponsor.

Any unused medicinal product or waste material should be disposed of in accordance with local requirements.

Further guidance and information for the final disposition of unused IMP are provided in the Investigator Manual (or equivalent document).

#### **7.1.4. Recall of IMP**

Instructions (actions to be taken by site) in the case of IMP recall are provided in the Investigator Manual (or equivalent document).

### **7.2. Administration and Dosage**

For Phase II, patients were randomized to either receive BSC + IFX-1 in treatment Arm A or BSC alone in treatment Arm B. The first dose of IFX-1 was administered at Cycle 1 Day 1.

For Phase III, patients are randomized to either receive SOC + IFX-1 in treatment Arm A or SOC + Placebo in treatment Arm B. The first dose of IFX-1 or Placebo is administered at Day 1. SOC may start at any time according to their administration schedule.

Close observation of IFX-1 or Placebo infusion(s) is required for monitoring of potential infusion reactions. Appropriate treatment for potential infusion reactions must be available during this time.

## **7.2.1. Treatment Administered**

### **7.2.1.1. Phase II**

[figure not shown]
IFX-1 800 mg was administered for a maximum of 7 doses over a period of 29 days as a 30-minute IV infusion. However, given the variability of infusion pumps from site to site, a window between 5 minutes and +10 minutes was permitted (i.e., infusion time was 30 minutes (5 min/+10 min). IMP administrations for Phase II are detailed in Figure 1.

The first 5 treatments at days 1, 2, 4, 8, and 15 were administered to all patients randomized into Arm A. Treatment at day 22 was only administered in the event that a patient had not been extubated and discharged from ICU. In case a patient's clinical situation worsened after day 8, although an initial clinical benefit was observed, one additional administration of IFX-1 between day 11 and 13 could have been given at investigator discretion.

### **7.2.1.2. Phase III**

[figure not shown]
Patients will be treated with a maximum of 6 IV doses of IFX-1 800 mg (Arm A) or placebo (Arm B) administered as a 30-60-minute IV infusion. The 6 treatments are at days 1, 2, 4, 8, 15, and 22 as long as the patient is still in the hospital, even if discharged from ICU. IMP administrations for Phase III are detailed in Figure 2.

Figure 1 Patient Calendar: IMP Administrations – Phase II

D = day; D/C = discharge; EOS = end of study; EOT = end of treatment; FUV = follow-up visit; IMP = investigational medicinal product

**Figure 2 Patient Calendar: IMP Administrations – Phase III**

D = day; FUV = follow-up visit; ICU = intensive care unit; IMP = investigational medicinal product

## **7.2.2. Treatment Modification**

This protocol allows some alteration from the currently outlined dosing schedule, but a dose reduction of IMP is generally not allowed.

Adverse events leading to treatment modifications will be graded as mild, moderate, severe, or life-threatening based on the investigator's assessment, using the definitions provided in Section 9.2.2.

In case of toxicity, IMP dosing can be held by a maximum of 1 week. If therapy is continued during this time span, dosing will resume at the initially planned next dosing day according to the initial schedule and allowed administration window.

For treatment discontinuation criteria, see Section 7.2.4.

### **7.2.2.1. Infusion Reactions**

IFX-1 may cause infusion reactions, including severe or life-threatening hypersensitivity or anaphylactic reactions. Signs and symptoms of infusion reactions usually develop during or shortly after drug infusion and generally resolve completely within 24 hours of completion of infusion with or without adequate medication. Dose modification criteria for infusion reactions are listed in Appendix 5, Table 6.

### **7.2.3. Re-dosing Criteria**

The following criteria must be fulfilled to allow for re-dosing of study drug:

- Absence of treatment discontinuation criteria (see Section 7.2.4).

### **7.2.4. Treatment Discontinuation Criteria**

Discontinuation of study treatment does not represent withdrawal from the study. See Section 5.6.1.1 (for Phase II) or Section 5.6.2.1 (for Phase III) for the end of treatment definition and procedures.

In general, patients should be treated with IMP until unacceptable toxicity, completion of the planned treatment, or death.

Possible reasons for treatment discontinuation for individual patients are:

- Clinical deterioration
- Study participation consent withdrawal (see Sections 5.6.1.3 and 5.6.2.3)
- Transfer of patient to another hospital

- Safety:
  - moderate infusion reactions despite adequate premedication (see Appendix 5, Table 6)
  - severe or life-threatening infusion reactions (see Appendix 5, Table 6)

### 7.3. Premedication and Postmedication

Routine premedication is not required prior to the first dose of IMP.

Patients with mild or moderate infusion reaction following IMP administration may continue to receive IMP with close monitoring; premedication with antipyretic and antihistamine may be considered.

Patients should be observed for 60 minutes, or longer per clinical judgment, after IMP administrations.

Treatment guidelines in case of occurrence of infusion reactions are detailed in Appendix 5, Table 6.

### 7.4. Prior and Concomitant Medication/Treatments

In Phase III of the study, in addition to the IMP, all patients will receive SOC for treatment of COVID-19, which includes VTE prophylaxis with anticoagulants at a minimum. Other international or country-specific recommended treatments for COVID-19 per the locally adopted treatment recommendations (including but not limited to corticosteroids, remdesivir, and other local SOC) are allowed as concomitant medications. SOC treatment start and stop is not defined by the protocol and can start at any time. SOC treatment will be given according to investigator's discretion.

Reporting of prior and concomitant medications will follow special considerations for the ICU setting, as described in Appendix 12.

Reportable medications or vaccinations that the patient is receiving within 7 days prior to randomization and up to 30 days after the last dose of study treatment should be recorded along with:

- Reason for use
- Dates of administration including start and end dates

The medical monitor should be contacted if there are any questions regarding concomitant or prior therapy.

#### 7.4.1. Prohibited Concomitant Medication/Treatment

Medications or vaccinations specifically prohibited in the exclusion criteria (see Sections 6.1.2 and 6.2.2) are not allowed during the ongoing study. If there is a clinical indication for any medication or vaccination specifically prohibited during the study, discontinuation from study therapy may be required. The investigator should discuss any questions regarding this with the medical monitor. The final decision on any supportive therapy or vaccination rests with the investigator and/or the patient's primary physician. However, the decision to continue the patient on study treatment requires the mutual agreement of the investigator and the sponsor.

The following concomitant therapies or vaccinations are prohibited during the course of the study:

- Antineoplastic systemic therapy
- Investigational antibody treatments and other investigational agents (excluding IFX-1 but including SARS-CoV-2 multiplication inhibitor[s] or immunomodulator[s]) which are not approved or not included in locally adopted treatment recommendations for treatment of COVID-19 (e.g., WHO guidance, NIH COVID-19 treatment guidelines)
- Cytokine adsorption therapy

Patients who, in the assessment of the investigator, require the use of any of the aforementioned treatments for clinical management should be removed from the study.

All treatments that the investigator considers necessary for a patient's welfare may be administered at the discretion of the investigator in keeping with the community standards of medical care.

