## **Phase III: Emergency Identification of Investigational Medicinal Product**

Breaking of the treatment-assigned blind will be performed in the IWRS (please refer to the Interactive Response Technology Study User Guide for instructions on unblinding). Any premature breaking of the blind should be confined to emergency cases in which knowledge of the IMP received is necessary, e.g., to be able to provide appropriate emergency medical treatment. Before breaking the blind, the investigator should contact the medical monitor whenever possible, unless this would delay the emergency treatment. Subject safety must always be the primary consideration when determining whether to break the blind.

Investigators will be provided with the appropriate IWRS access to unblind the treatment assignment of an individual subject.

If a subject's treatment assignment is unblinded, the required personnel will receive an alert from the IWRS. In addition, the investigator must inform the medical monitor within 24 hours of breaking the blind and the subject will be discontinued from further IMP treatment. The date and reason why the blind was broken must be provided by the investigator and recorded in the source documentation and in the eCRF, as applicable.

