### 5.6.2.2. End of Study

The end of study for the individual patient is defined as the date of the last contact of the follow-up period (i.e., 60 days after randomization), date of death, date of consent withdrawal from study participation (see Section 5.6.2.3), or the date of last contact when patients are lost to follow-up (see Section 5.6.2.4), whatever occurs earliest.

The entire study will end when all patients have discontinued IFX-1 AND all patients ended the study as described above.

The sponsor may prematurely terminate the study at any time earlier than planned for the following reasons:

- Unacceptable toxicity
- Administrative reasons

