### 5.6.2.3. Consent Withdrawal/Discontinuation of Study Participation

A patient may withdraw from the entire study at any time at his/her own request without the need to provide any reason(s).

If the patient withdraws /patient is withdrawn by legal representatives/relatives from study participation, the sponsor may retain and continue to use any data collected before such a withdrawal of consent. However, in the case of deferred informed consent, if the consent is not obtained or if a legal representative denies the patient's participation in the study, the patient is excluded and data will no longer be used, except if local regulations would permit the use of such data in this situation (see Section 6.3). Patients (or legal representatives/relatives) who wish to withdraw consent/discontinue the study while still on treatment should be encouraged by the

investigator to perform the FUV for their own safety before any further data collection will be stopped.

If a patient (or legal representatives/relatives) withdraws from the study, he/she may request destruction of any samples taken and not tested, and the investigator must document this in the site study records.

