### 9.3. Death Reporting

The site should follow all patients for survival and collect information around the death on the appropriate eCRF form until the end of the study.

Primary cause of death should be reported in AE section and SAE form, as well as appropriate eCRF section(s). If symptoms of disease progression occurred and constitute the primary cause of death, these symptoms could be reported as fatal (S)AE (see Section 9.2.2).

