### **9.5.2.      Pregnancy Reporting**

If the patient or partner of a patient participating in the study becomes pregnant during treatment or within 30 days after the last dose of treatment with IFX-1, the investigator should report the pregnancy to [QLS\\[contact]](mailto:[contact]) via e-mail within 24 hours of being notified. The safety vendor will then forward the pregnancy reporting form to the investigator for completion. In case that e-mail contact is not possible, the site can provide an initial pregnancy report in the SAE section of the SAE form and transmit this via the SAE FAX line: [contact].

A patient becoming pregnant while on IMP will immediately be discontinued from treatment and the EOT visit will be performed.

The patient or partner should be followed by the investigator until completion of the pregnancy. If the pregnancy ends for any reason before the anticipated date, the investigator should notify the sponsor. At the completion of the pregnancy, the investigator will document the outcome of the pregnancy. If the outcome of the pregnancy meets criteria for immediate classification as an SAE (i.e., postpartum complication, spontaneous abortion, stillbirth, neonatal death, or congenital anomaly), the investigator should follow the procedures for reporting as SAE.

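### Section 7.4.1 takes patients who need a prohibited treatment out of the study rather than off study drug; this contradicts the survival follow-up rule and puts confirmed-alive status at day 28 and vital status at day 60 at risk, with a small expected effect

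*Combined protocol and SAP*

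**What the plan says.** All references are to protocol Version 4.0, Phase III.

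- **Section 7.4.1** lists antineoplastic systemic therapy, COVID-19 agents outside approval or local guidelines, and cytokine adsorption as prohibited. It then says that patients who, in the investigator's assessment, "require the use of any of the aforementioned treatments for clinical management should be removed from the study".
- **The same section, first paragraph**, gives a milder consequence: "discontinuation from study therapy may be required". It also allows dosing to continue if investigator and sponsor agree. Its closing sentence leaves any treatment needed for the patient's welfare to the investigator.
- **Section 9.3**: "The site should follow all patients for survival and collect information around the death", up to the end of the study.
- **Section 5.6.2.2** defines a patient's end of study as the last follow-up contact (day 60), death, "date of consent withdrawal from study participation (see Section 5.6.2.3), or the date of last contact when patients are lost to follow-up". Removal by the investigator is not listed.
- **Sections 5.6.2.1 and 7.2.4**: "Discontinuation of study treatment does not represent withdrawal from the study".
- **Two other events that end dosing** stop the drug only. After emergency unblinding "the subject will be discontinued from further IMP treatment" (Section 5.1.2), and Section 9.5.2 says "A patient becoming pregnant while on IMP will immediately be discontinued from treatment".
- **Sections 5.6.2.1 and 8.2.2.3** schedule survival contacts at days 28 and 60.
- **Section 10.2.2** keeps every randomized patient in the FAS except those randomized in error and never dosed.
- **Section 10.2.3.1** gives one censoring rule, at day 28. Section 10.2.3 leaves missing data to the SAP.

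**The concern.** The primary endpoint is all-cause death by day 28 and the first secondary endpoint is death by day 60. Both can be ascertained whatever other treatment a patient receives, so ending follow-up because of a prohibited treatment gains nothing.

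A site that takes the removal sentence literally may make no day-28 or day-60 contact for a patient who remains in the analysis set. The nearest text on leaving the study, Section 5.6.2.3, urges such patients to "perform the FUV for their own safety before any further data collection will be stopped". That paragraph concerns patients or representatives who choose to leave, but a site could read removal the same way.

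The trigger is clinical need, so removed patients may differ in prognosis from the rest. That is an inference; the documents do not state it. Nor are such patients replaced: the 10% allowance in the synopsis covers only randomization in error and consent withdrawn within 48 hours, while the power statement assumes at least 360 patients evaluable for the primary endpoint.

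**Working it through.** **1. Which instructions conflict.** The removal sentence directly contradicts its own section's first paragraph and Section 9.3. Against Sections 5.6.2.1, 7.2.4 and 5.6.2.2 it is only out of line. The first two say that stopping drug is not withdrawal, without mentioning prohibited treatment. The third omits removal from the list of study ends, which favours continued follow-up.

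**2. What safety reporting still captures.** Sections 9.1 and 9.1.1 require all serious events to be reported until 30 days after the last dose, and Section 9.2.1 requires fatal events within 24 hours.

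- Dosed on day 1 only: 1 + 30 = day 31, past the primary endpoint.
- Last dose on day 8: 8 + 30 = day 38.
- Last possible dose, day 22: 22 + 30 = day 52, short of day 60.

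Beyond that window, the opening of Section 9 says deaths in follow-up are collected, but Section 9.1.1.1 mentions only drug-related serious events after discharge. Event reporting also never confirms that a patient is alive. The exposed items are therefore alive status at day 28 and vital status at day 60.

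**3. The plan's own power figure.** Inputs from Section 10.2.1 and the synopsis: 30% vs 15% mortality, one-sided 2.5%, n = 180 per arm, stated power 90%.

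- SE under the null = √(2 × 0.225 × 0.775 / 180) = 0.0440
- SE under the alternative = √((0.30 × 0.70 + 0.15 × 0.85) / 180) = 0.0433
- Uncorrected: Φ((0.15 − 1.96 × 0.0440) / 0.0433) = 92.9%
- Continuity-corrected, with 0.15 − 1/180 in place of 0.15: 91.0%, close to the stated 90%

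**4. Outcomes lost without regard to prognosis.** The share is assumed; n is multiplied by (1 − share) in the uncorrected formula.

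| Share lost | Patients of 360 | Power |
|---|---|---|
| 0 | 0 | 92.9% |
| 1% | 3.6 | 92.7% |
| 2% | 7.2 | 92.5% |
| 5% | 18 | 91.7% |
| 10% | 36 | 90.2% |

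**5. A pessimistic bound: every death after removal is lost.** This is a simulated treatment-only Cox model (age omitted) with 180 per arm and 40,000 replicates. Assumptions: removal spread over days 1 to 14, threefold death hazard afterwards, censoring at removal. Monte Carlo SE is about 0.13 points for power and 0.08 for type I error. Step 2 makes this worse than the documents suggest for day 28.

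| Removal, IFX-1 / placebo | Truth | Full follow-up | Censored at removal |
|---|---|---|---|
| 1% / 1% | 15% vs 30% | power 93.3% | 92.9% (1.4 deaths lost) |
| 2% / 2% | 15% vs 30% | power 93.2% | 92.5% (2.8 deaths lost) |
| 2% / 1% | 30% both | type I 2.5% | 2.8%; futility stop 50.1% to 48.4% |
| 1% / 2% | 30% both | – | type I 2.1% |
| 10% / 10% | 15% vs 30% | power 93.0% | 89.0% |
| 10% / 5% | 30% both | – | type I 4.5% |

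The documents do not support the 10% rows. With 10% / 5% removal but no excess hazard, type I error is 2.4%, so bias needs both unequal removal and worse prognosis.

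**6. One patient near the boundary** (pooled two-proportion z, placebo vs IFX-1, critical value 1.96).

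- Complete data, 54/180 vs 38/180: (0.3000 − 0.2111) / 0.0460 = 1.93
- One IFX-1 death unascertained, 54/180 vs 37/179: (0.3000 − 0.2067) / 0.0459 = 2.03
- One placebo survivor unconfirmed and dropped, 54/179 vs 38/180: (0.3017 − 0.2111) / 0.0461 = 1.97
- One IFX-1 survivor unconfirmed and dropped, 54/180 vs 38/179: (0.3000 − 0.2123) / 0.0461 = 1.90

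An unconfirmed survivor, the more likely loss, shifts z by about 0.03, against about 0.10 for a lost IFX-1 death.

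**The case against.** The best defence is that removal does not in practice end ascertainment of death. Serious and fatal events must be reported for 30 days after the last dose, with no condition that the patient still attends visits. That covers day 28 even for a patient dosed once. Section 5.6.2.2 does not recognise removal as an end of study, so a removed patient who has not withdrawn consent still reaches day 60 or death. Section 5.6.2.3 ties leaving to the end of data collection only when the patient or representative chooses to leave. The closing sentence of Section 7.4.1 and its sponsor-agreement route make compulsory removal a less natural reading. The prohibited list is narrow, guideline therapy is allowed (Section 7.4), active malignancy is excluded at entry (Section 6.2.2), and Phase III is double-blind. The example in step 6 was chosen to sit at the boundary; one missing outcome from any cause would do the same.

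Most of this stands. A reader might infer that removed patients are censored at removal and that their deaths vanish from the primary Cox model. The documents do not support that: no such censoring rule exists, and safety reporting should capture most deaths to about day 31. What the defence does not settle is the conflict within Section 7.4.1 and with Section 9.3. Event reporting also cannot show that a silent patient is alive, and the text on deaths after the reporting window is not uniform up to day 60.

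**Conclusion.** The instruction is internally inconsistent and should be corrected. Followed literally, it could leave alive status at day 28 unconfirmed and vital status at day 60 uncollected for patients who count in the FAS. A later SAP could choose how to handle those gaps but could not fill them.

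The expected effect is small. At assumed removal rates of 1% to 2%, even losing every later death costs 0.4 to 0.7 points of power and leaves one-sided type I error between 2.1% and 2.8%. Only a result very close to the boundary could change. Material type I error inflation would need frequent and unequal removal in a double-blind trial, together with worse prognosis and censoring at removal; the documents establish none of these. Removal rate, prognosis and arm difference are all assumptions here, because the documents give no figure for any of them.

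**What to change.** Replace the removal sentence in Section 7.4.1 with:

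> Such patients may be discontinued from IMP but remain in the study, are followed for vital status at days 28 and 60, and are analysed in the FAS as randomized without censoring at the start of the prohibited treatment.

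The cost is one sentence and no added visit, since both contacts are already scheduled. Appendix 2 requires ethics approval for amendments, so the change can go with the next one. Until then, a clarification to sites citing Section 9.3 would protect follow-up. The small downside is that some analysed patients will have received prohibited therapy.
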